**Exclusion Criteria:**

- Patients for whom clinically indicated endoscopy is not safe. Patients who have small caliber esophagus, an esophageal stricture that will not permit passage of the gelatin capsule or are unable to swallow the capsule. Patients who have taken any antithrombotic medication within 10 days of the procedure.

- Vulnerable populations, such as those with diminished mental acuity, will be excluded.  
Patients with known Lidocaine/Acetylcysteine allergies

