**Collaborators:**

[name]  
[name]  
[name], PhD  
[name]  
[name]

**Study Coordinator:** [name], CCRP

Division of Gastroenterology & Hepatology, Mayo Clinic Rochester, MN

Eosinophilic esophagitis is a relatively new disease in which esophageal eosinophilia leading to inflammation and stricture formation results from exposure to food antigens. Although it would seem logical that identification and removal of food antigens would be the definitive treatment, this is more easily said than done.

There are several reasons for this:

- Current available allergen testing, mostly through blood and skin, do not reliably reflect specific allergen sensitivity in the esophagus.
- As there has not been a non-invasive test to determine the esophageal response to single food allergens, clinicians have had to choose between allergen avoidance therapy because it is too cumbersome or performing serial and at times numerous endoscopies and biopsies to fully evaluate a range of potential foods that may trigger the inflammatory response.
- Treatment of eosinophilic esophagitis is also further hampered by a distinct lack of symptoms in adults due to what is typically a silent inflammatory response until stricture formation and subsequent dysphagia and impaction occur.
- Furthermore, adult patients with this disease typically accommodate by careful chewing and slow eating such that an absence of symptoms commonly underestimates the severity

of disease. As a result, an invasive test that reliably determines esophageal eosinophilic would be extremely valuable for monitoring disease activity and the response to food allergen withdrawal or introduction.

Cytosponge is an ingestible gelatin capsule containing a compressed mesh attached to a string. The capsule is swallowed and once in the stomach, the gelatin dissolves and a spherical mesh of 3 cm diameter is released. The mesh is withdrawn through the mouth by the attached string and a cytologic specimen is collected.

Current cytosponge from University of Cambridge

Covidien Cytosponge

In a recent study evaluating the Cytosponge in patients with Barrett's esophagus, excellent results were achieved with a the sensitivity and specificity of the test was 73.3% (95% confidence interval 44.9% to 92.2%) and 93.8% (91.3% to 95.8%) for 1 cm or more circumferential length and 90.0% (55.5% to 99.7%) and 93.5% (90.9% to 95.5%) for clinically relevant segments of 2 cm or more.

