### **Methods:**

- Patients with eosinophilic esophagitis and health controls, (patients without esophageal symptoms such as GERD or dysphagia), will be enrolled.
- Patients with EoE will be having a clinically indicated upper endoscopy and biopsies either for initial diagnosis or for monitoring the activity of their disease.
- All patients will be asked to be fast, no solid food 8 hours prior to swallowing the cytosponge, can drink clear liquids up to 2 hours prior to swallowing the cytosponge
- The EoE subjects two hours prior to endoscopy will be asked to swallow the Cytosponge. Briefly, the capsule and bunched up string are swallowed with water. Two hours is chosen as the time interval because water will likely be needed to swallow the capsule and this is the standard time allowed for to last safely consume a clear liquid prior to endoscopy.
- Controls will be will have the same fasting instructions but will not be required to be having and endoscopy.
- The string is held without any tension to allow the capsule to move into the stomach. The patient holds onto the string for five minutes after ingestion to allow the capsule to dissolve in the proximal stomach, where a spherical mesh of 3 cm diameter is released.
- The back of the throat is then sprayed with 1% lidocaine and the expanded mesh withdrawn by pulling on the string with the patient's head in an extended position.
- After retrieval the string is cut and the Cytosponge containing the cytological specimen placed in preservative fluid and kept at room temperature until transportation to the laboratory.
- The whole process of administering the Cytosponge, including instructing the patient, takes less than 10 minutes.
- Following this, the clinically indicated endoscopy will be performed. The cytology specimens will be reviewed by one pathologist who will read them blindly without knowledge of the results of the biopsy specimens. The cytology specimens will be

compared to the biopsy in terms of esophageal eosinophil presence and density. A scoring system for cytology will be devised.

- Samples from the University of North Carolina will be sent to the Mayo Clinic to be reviewed by the same pathologist.

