**Study flow:**

- The study coordinator will look for patients being seen in Esophageal clinic with the indication of EoE or healthy controls (patients without esophageal symptoms such as GERD or dysphagia)
- When the physician has an EoE patient scheduled for a clinically indicated upper endoscopy, to diagnose or monitor their disease, these patients will be approached by the study coordinator to see if they are interested in the cytosponge study?
- Subjects willing to swallow the cytosponge that do not have esophageal symptoms will be approached by the study coordinator.
- Patients with EoE will then be scheduled to come to Gonda 9s two hours prior to the endoscopy. Healthy controls will be scheduled to come to Gonda 9 at their convenience as long as they adhere to the fasting instructions.
- The physician will have the patient swallow the Cytosponge.
- The patient holds onto the string for five minutes after ingestion to allow the capsule to dissolve in the proximal stomach, where a spherical mesh of 3 cm diameter is released.
- The back of the throat is then sprayed with 1% lidocaine and the expanded mesh withdrawn by pulling on the string with the patient's head in an extended position.
- After retrieval the string is cut and the Cytosponge containing the cytological specimen placed in preservative fluid and kept at room temperature until transportation to the laboratory.
- The whole process will take approximately 10 minutes.
- A throat swab for collection will also be performed at this time to be processed for bacterial population of the esophageal mucosa.
- Following this, the clinically indicated endoscopy will be performed. Prior to biopsies we will do a brushing of the esophagus.
- The cytology specimens will be reviewed by one Mayo pathologist who will read them blindly without knowledge of the results of the biopsy specimens.
- The cytology specimens will be compared to the biopsy in terms of esophageal eosinophil presence and density. A scoring system for cytology will be devised.
- We will do further EoE/allergy analysis with FFPE slides including EDN and tryptase staining.
- When the Mayo pathologist have completed their analysis, slides and part of the uncut blocks will be sent to [name] lab looking at reproducibility of results, evaluation of the mucosal microbiome by sequencing and additional biomarker studies including RNA, methylation and protein analyses.

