## **Weaknesses**

The main weaknesses of this study will be the potential inability of a patient to swallow the capsule or risk of impacting (though the capsule will dissolve and it will be easily removable).

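### Is the stricture and swallowing exclusion unworkable because the capsule is taken two hours before the endoscopy?

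*Protocol*

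**What the plan says.** The Exclusion Criteria bar patients with "small caliber esophagus, an esophageal stricture that will not permit passage of the gelatin capsule or are unable to swallow the capsule". They give no time at which this is judged and no source of evidence. Unlike the allergy exclusion in the same list, this one is not limited to known findings.

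Methods admits EoE patients whose endoscopy is "either for initial diagnosis or for monitoring the activity of their disease". Study flow describes the same population: "When the physician has an EoE patient scheduled for a clinically indicated upper endoscopy, to diagnose or monitor their disease".

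The order of procedures is fixed. Methods states: "The EoE subjects two hours prior to endoscopy will be asked to swallow the Cytosponge". Study flow places the capsule, its retrieval and a throat swab first, and then: "Following this, the clinically indicated endoscopy will be performed". Under Methods, controls "will not be required to be having and endoscopy". No earlier examination of the esophagus is described for anyone.

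The background text at the start of the protocol says that in adults "an absence of symptoms commonly underestimates the severity" of the disease. Weaknesses names as the main limits of the study "the potential inability of a patient to swallow the capsule or risk of impacting".

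**The concern.** An exclusion criterion is normally settled before the study procedure. Here, a patient at first diagnosis may have no earlier endoscopy on file, and the examination that would show a narrow esophagus comes after the capsule. The background text casts doubt on symptoms as a substitute. Weaknesses then lists, as things that may happen during the study, much the same conditions that the Exclusion Criteria are meant to keep out.

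Two things could be at stake. First, someone who meets the exclusion might be given the capsule before anyone could know it. Second, the Specific Aim is sensitivity and specificity of the Cytosponge against endoscopy and biopsy. If eligibility is settled by one of those two tests, a failed attempt could be relabelled as an ineligible patient and drop out of the count. Late findings of stricture at endoscopy would arise mainly in EoE patients, since controls need not have endoscopy. Two sites pool their data and might handle such cases differently.

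**Working it through.** No formula applies. The question is what can be known, and when. The inputs are the sections cited above.

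**Order of events for an EoE subject** (Methods, Study flow), with endoscopy at time 0:

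1. Approach by the coordinator, after a physician has scheduled the endoscopy.
2. Capsule swallowed at 0 − 2 h = −2 h.
3. Mesh withdrawn after the five-minute wait; throat swab taken.
4. Endoscopy with brushing and biopsies at 0 h.

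The study endoscopy can therefore inform the exclusion before the capsule in 0 EoE subjects. This is as true of monitored patients as of new ones. The groups differ only in what may already be on record.

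**Each part of the criterion against each group:**

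| Part | EoE, first diagnosis | EoE, monitored | Controls |
|---|---|---|---|
| Small caliber or stricture, already recognised | Can be applied at entry | Can be applied at entry | Can be applied at entry |
| Small caliber or stricture, not recognised | No described step before the capsule reveals it | An earlier endoscopy may help | Endoscopy not required |
| Unable to swallow the capsule, already evident | Can be applied at entry | Can be applied at entry | Can be applied at entry |
| Unable to swallow the capsule, not evident | Shown only by the attempt | Shown only by the attempt | Shown only by the attempt |

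The first and third rows can be applied at entry in every group. The fourth row does not depend on endoscopy in any group, so neither the two-hour order nor first diagnosis is its cause. What is left of the concern is one cell: an unrecognised narrowing in a patient at first diagnosis.

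**Are symptoms useless for that cell?** The sentence about absent symptoms concerns severity of disease in general, in adults who adapt by chewing carefully and eating slowly. The bullet before it describes inflammation that is usually silent up to the point where strictures form and dysphagia and impaction follow. The protocol thus ties the excluded condition itself to symptoms. They are an imperfect screen, but they carry information.

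**Do Exclusion Criteria and Weaknesses clash?** Weaknesses goes on to note that the capsule dissolves and can be removed easily. Excluding recognised cases while admitting that some will be missed is consistent.

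**Size.** The protocol gives 130 participants at Mayo and 180 in all. It gives no EoE-to-control split, no share at first diagnosis, and no rate of narrowing or failed swallowing. A bias in sensitivity or specificity cannot be derived, and a guessed rate would tell the reader nothing about this trial.

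**The case for a change.** The best case for a change is that the authors wrote *known* for allergies and left it out here, so the exclusion covers undiscovered narrowing too, and for new patients no described step could find it. When and from what source eligibility is judged belongs in a protocol, and a sentence would cost little. Without it, two sites could treat a failed attempt differently.

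The facts in this stand. The inference from the missing word is weak in a text drafted this loosely. An exclusion without a stated source is ordinarily judged on what is known at entry, and nothing in Methods or Study flow prevents that. Patients come from an esophageal clinic, a physician has scheduled their endoscopy, and a physician oversees the swallowing.

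The point about failed attempts would matter if the protocol told investigators to drop such patients. It does not. How failed attempts enter sensitivity and specificity is commonly left to the SAP, which is not at hand. Keeping the outcome of every capsule attempt by group, so that failures stay visible, is ordinary good practice and is open to the analysts under the present text.

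**Conclusion.** No change to the plan follows. The sequence is as described: for EoE patients at first diagnosis, no stated step before the capsule would reveal a narrowing that nobody had recognised. But the sections do not contradict one another. The criterion works at entry for recognised cases, the protocol acknowledges the remaining risk, and the swallowing part would be settled no earlier by a different order of procedures.

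An added sentence would only record when the criterion is judged and on what evidence. It would add no examination, and no bias has been shown that it would remove.

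This conclusion rests on two assumptions: that the exclusion is read in the usual way, as what is known before the attempt, and that failed attempts are recorded and not silently reclassified as ineligible. The text is compatible with both, although it states neither. Whether any clinical assessment should come before the capsule is for the clinical team.

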There was also overall excellent tolerance by patients using the Cytosponge. As a result, one might wonder if the Cytosponge would similarly be a reliable relatively non-invasive tool for evaluating patients with eosinophilic esophagitis.

**Specific Aim:** To evaluate the sensitivity and specificity of Cytosponge when compared to upper endoscopy and biopsies/swab testing in patients undergoing clinically indicated endoscopy for evaluation of eosinophilic esophagitis and healthy controls

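### Could the exclusion for being unable to swallow the capsule remove failed attempts and flatter the sensitivity?

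*Protocol*

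**What the plan says.** The Exclusion Criteria list, in one sentence, a small caliber esophagus, "an esophageal stricture that will not permit passage of the gelatin capsule or are unable to swallow the capsule". No time point is attached. A later entry in the same list does refer to prior knowledge: "Patients with known Lidocaine/Acetylcysteine allergies".

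Methods and Study flow place the first contact with the capsule at the study visit, which for EoE patients is two hours before a clinically indicated endoscopy. Study flow says "The physician will have the patient swallow the Cytosponge" and describes no earlier swallowing assessment. It then states: "The cytology specimens will be compared to the biopsy in terms of esophageal eosinophil presence and density". Under Methods, controls "will not be required to be having and endoscopy".

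The Weaknesses section names "the potential inability of a patient to swallow the capsule or risk of impacting" as the main weaknesses. The only remark on how well the device is tolerated is in the background text, on the earlier Barrett's study: "There was also overall excellent tolerance by patients using the Cytosponge".

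**The concern.** Most exclusions in the list can be settled before the visit. Inability to swallow this capsule may show only on trying. Read literally, the clause also describes a person who was enrolled, attempted the capsule and failed. If that person were reclassified as ineligible, sensitivity would be conditional on a completed test.

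Failures would plausibly fall more on EoE patients, because the background links the disease to dysphagia and impaction while controls are chosen for having no dysphagia. EoE patients are the group that determines sensitivity, which with specificity is the study's one specific aim. The test is motivated by the burden of "performing serial and at times numerous endoscopies and biopsies to fully evaluate a range of potential foods", and a patient who yields no specimen gets no relief from that burden. The reported figure could then overstate the share of biopsy-positive patients the test finds, and a weakness the protocol itself names might not show in the results.

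**Working it through.** **Reading the sections together**

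1. The swallowing clause shares its sentence with small caliber esophagus and a blocking stricture. Both are features a patient brings to screening, and neither carries a word such as known. The missing qualifier is the usual style of the list, so the contrast with the allergy entry is weak evidence of a different intent.
2. If every failed attempt became an exclusion, inability to swallow would hardly be a weakness of the study. Listing it as one treats it as something that happens to participants. The two sections agree if known inability is screened out and unexpected failure is a limitation.
3. No sentence says that a failed attempt is removed or reclassified. Study flow says how specimens are compared with biopsy and is silent on people without one.
4. Suppose the clause were limited to inability known beforehand. A person who then failed would still have no cytology to compare. Sensitivity would change only if a separate rule counted that person as not detected. The result depends on that rule, not on the eligibility wording.
5. The EoE patients' endoscopy is clinically indicated, so a biopsy result can exist whether or not the capsule goes down. Analysts can therefore form an all-attempts figure under the present design.

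**Size, with every input assumed**

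The protocol gives no failure rate, target sensitivity or split between EoE patients and controls, so there is no stated figure to reproduce. Let S be sensitivity among completers and f the share of biopsy-positive patients whose attempt fails. Counting failures as not detected,

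sensitivity among all attempts = S × (1 − f), a shift of S × f.

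| S | f = 2% | f = 5% | f = 10% | f = 20% |
|---|---|---|---|---|
| 75% | 73.5% | 71.2% | 67.5% | 60.0% |
| 80% | 78.4% | 76.0% | 72.0% | 64.0% |
| 85% | 83.3% | 80.8% | 76.5% | 68.0% |

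At S = 80% the shift is 0.80 × 0.02 = 1.6 points for 2% failures and 0.80 × 0.10 = 8 points for 10%.

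For scale, the Wilson 95% interval around 80%, with assumed numbers of biopsy-positive completers among the 180 subjects stated under Recruitment:

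| Completers | 95% interval | Half-width |
|---|---|---|
| 50 | 67.0% to 88.8% | 10.9 points |
| 75 | 69.6% to 87.5% | 8.9 points |
| 100 | 71.1% to 86.7% | 7.8 points |

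The shift is well inside sampling error at 2% and about equal to the narrowest half-width at 10%. The reported tolerance and the exclusion of small-caliber and blocking-stricture patients make the low end more plausible, though that report comes from a different population.

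**The case for a change.** The best argument for acting is that eligibility is protocol content. If failures left through an exclusion, a rule for failed tests in the analysis plan might never reach them. The protocol foresees failed swallows, describes no check before the visit, and contains a clause whose words fit the people who fail. The clarification would also be cheap: a phrase in the exclusion list and an extra reported figure, with no new procedure.

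Part of this stands. The clause has no time point, no other section supplies one, and the arithmetic is correct. A reader could fairly ask for a clarifying phrase as a matter of drafting. But the argument needs someone to apply a screening criterion after the attempt, which nothing in the document directs and the Weaknesses section speaks against. The cost is also more than one figure, because the full proposal adds completion by group and by biopsy result as well as a second sensitivity estimate.

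The choice of estimand is open too. Accuracy among completed tests, with completion reported beside it, is a legitimate target: a person who cannot swallow receives no result, which is not the same as a false negative. An all-attempts sensitivity next to a completers-only specificity would put the two headline figures on different bases.

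**Conclusion.** No change to the plan is needed. The exclusion lacks a time point, but its ordinary reading as a screening criterion agrees with the Weaknesses section, and no stated rule removes failed attempts. How such attempts count towards sensitivity is an analysis-set question that the statistical analysis plan, not available here, may settle; analysts can be expected to report completion alongside accuracy. The possible overstatement cannot be derived from the protocol. Taking 80% sensitivity among completers, it is 1.6 points at 2% failures and 8 points at 10%, and it arises only if failures are in fact dropped. A clarifying phrase would be harmless and optional. The conclusion would differ if the analysis plan or the conduct of the study did treat failed attempts as ineligible.

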**Study flow:**

- The study coordinator will look for patients being seen in Esophageal clinic with the indication of EoE or healthy controls (patients without esophageal symptoms such as GERD or dysphagia)
- When the physician has an EoE patient scheduled for a clinically indicated upper endoscopy, to diagnose or monitor their disease, these patients will be approached by the study coordinator to see if they are interested in the cytosponge study?
- Subjects willing to swallow the cytosponge that do not have esophageal symptoms will be approached by the study coordinator.
- Patients with EoE will then be scheduled to come to Gonda 9s two hours prior to the endoscopy. Healthy controls will be scheduled to come to Gonda 9 at their convenience as long as they adhere to the fasting instructions.
- The physician will have the patient swallow the Cytosponge.
- The patient holds onto the string for five minutes after ingestion to allow the capsule to dissolve in the proximal stomach, where a spherical mesh of 3 cm diameter is released.
- The back of the throat is then sprayed with 1% lidocaine and the expanded mesh withdrawn by pulling on the string with the patient's head in an extended position.
- After retrieval the string is cut and the Cytosponge containing the cytological specimen placed in preservative fluid and kept at room temperature until transportation to the laboratory.
- The whole process will take approximately 10 minutes.
- A throat swab for collection will also be performed at this time to be processed for bacterial population of the esophageal mucosa.
- Following this, the clinically indicated endoscopy will be performed. Prior to biopsies we will do a brushing of the esophagus.
- The cytology specimens will be reviewed by one Mayo pathologist who will read them blindly without knowledge of the results of the biopsy specimens.
- The cytology specimens will be compared to the biopsy in terms of esophageal eosinophil presence and density. A scoring system for cytology will be devised.
- We will do further EoE/allergy analysis with FFPE slides including EDN and tryptase staining.
- When the Mayo pathologist have completed their analysis, slides and part of the uncut blocks will be sent to [name] lab looking at reproducibility of results, evaluation of the mucosal microbiome by sequencing and additional biomarker studies including RNA, methylation and protein analyses.
- We will send samples from a cell block made from the cytology fluid from the cytosponge and a portion of the primary cytosponge placed in RNAlater solution. For extra-cellular RNA signature analysis with possible detection of EoE specific lumen protein products proposed to [name] lab at the University of Cincinnati.
- FFPE RNA from the concurrent biopsies at the time of the EGD if available

as biopsy tissue represents the source of the dislodged cells/tissue pieces by the cytosponge. Parallel comparison will provide key clue to validate the new diagnostic approach.

- H+E sections will be digitized. Cytosponge and esophageal biopsy sections will be stained for EPX and analyzed.

